#### **15.4.3 Secondary efficacy analysis**

The secondary efficacy endpoints will be 5 and 10 years overall survival and 10 years disease free survival, comparing exemestane vs. tamoxifen followed by exemestane as estimated from the Kaplan-Meier curves for each treatment arm. The difference in 5 and 10 overall survival and 10 years disease free survival between the treatment arms will be reported, along with its standard error (SE) and an associated 95% confidence interval. In addition, patients will be followed up for a minimum of 10 years and long term outcomes will be reported.

For the primary efficacy analyses, Cox regression models will be used to explore the influence of stratification and prognostic factors on DFS. Each factor will be evaluated for inclusion in the multivariate model, and only factors significant at the 10% level will be considered. The secondary efficacy analysis, i.e. the results of the patients who received both medications sequentially due to the “cross-over” design, will be analysed on an exploratory basis since the proportional hazards model may not be appropriate for these patients.

### **15.5. Safety analysis**

Safety analyses will include all randomised subjects who received at least one dose of study medication. Adverse events will be recorded and graded according to the CTC classification system (Appendix 5 shows a selection).

The frequency and percentage of patients experiencing a specific adverse event will be tabulated by treatment group. Adverse events will be summarised by worst CTC grade and reported relationship with study group. In the cases that the adverse events or event frequencies are judged to be clinically important, a Chi-square test will be used to analyse the difference between the treatment groups.

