**Secondary endpoints**

- ❑ Overall Survival (OS)
- ❑ Incidence of second breast cancer (in contralateral breast)
- ❑ Safety and long-term tolerability of both regimens

Differences in outcome based on pathological subgroups will also be analysed and a quality of life (QOL) comparison between the two study arms undertaken (using the FACT-ES questionnaire).

[figure not shown]
**Study design** Phase III, open label, randomised, multicentre, international trial.

**Subject numbers** 8740 subjects globally, 1240 from the UK/ROI.

**Main selection criteria** Women with a histological/cytological diagnosis of early invasive breast carcinoma, completely resected, and who meet the following criteria:

- ❑ Postmenopausal
- ❑ ER/PgR-positive
- ❑ - Any node-positive cancer
  - Any cancer  $\geq$  3cm
  - Node-negative cancer, grade II or III and  $\geq$  1cm
- ❑ Adequate haematological, renal and hepatic function
- ❑ ECOG performance status 0, 1 or 2
- ❑ Patients must be randomised within 10 weeks surgery or completion of chemotherapy

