**Figure 1: Trial Data Flowchart**

Year						Follow-up (year 1 to 5)	Follow-up (year 6 to 10)
	1	2	3	4	5	6-10	11-15
Visit							
Within months	0	3	6	9	12	12-60	60 - 120
Medical history	X						
Initial data 	X						
Clinical examination	X	X	X	X	X	X	Follow-up should be carried out annually according to local policy
Events (if present)		X	X	X	X	X	
Co-medication 	X	X	X	X	X	X	
Adverse Events/SAEs 	X	X	X	X	X	X 	
Mammography	X					Local policy	
Quality of Life (QOL)	X	X			X		

Notes:

1. Type of primary surgery, tumour pathology and characteristics, pre-existing medical conditions.
2. Any medication **prescribed** and used for more than 7 consecutive days.
3. As described in section 12, 'Adverse Events'.
4. After completion of study treatment, adverse events need only be recorded if they occur within 30 days of the last dose of study medication (section 12).

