## **12. ADVERSE EVENTS: DEFINITIONS AND REPORTING**

### **12.1. Procedures for collecting Adverse Events**

All medical occurrences (which meet any of the following definitions) from the first dose of Investigational Medicinal Product (IMP) to 30 days after the last dose of IMP should be reported as adverse events and must be accurately recorded on the appropriate trial CRF and sent to the **TEAM** study office.

In addition, any known untoward event that occurs subsequent to the adverse event-reporting period that the Investigator assesses as possibly related to the IMP should also be considered an adverse event and reported accordingly.

Toxicities will be reviewed using the National Cancer Institute Common Toxicity Criteria (NCI CTC version 2.0). Appendix 5 shows a selection of the NCI CTC; a full list can be found in your Investigator Site File or you can request a copy from the CRCTU. Any toxicities incurred but not categorised by the NCI CTC should be graded by the physician and be recorded on the CRF using a scale of (1) mild, (2) moderate or (3) severe (as defined in Appendix 6). For each sign/symptoms, the highest grade observed since the last visit should be recorded.

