After considerable deliberation the **TEAM** trial has been amended so that women randomised to tamoxifen will be offered the opportunity to switch to exemestane after they have completed at least 2.5 years of tamoxifen therapy. The new design will allow us to determine the best way of using exemestane, which now has an established role. This does however require a larger sample size. It has been possible to introduce this change effectively for all patients since the first patients entered the trial less than 3 years from the change.

All patients in **TEAM** will be informed about this change and will all be re-consented. Women who are happy to switch from tamoxifen to exemestane will start to receive trial stock exemestane from their hospital pharmacy at the appropriate scheduled visits and should stop tamoxifen after they have their exemestane prescribed. Some patients may prefer to stay on tamoxifen in which case they will come 'off study' but we will continue to follow these patients and perform an intent to treat analysis. For women allocated exemestane there are no direct consequences to this change and they will continue to be treated with exemestane as now. Patients experiencing difficulty with exemestane should be referred back to hospital for advice.

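### Section 15.5 compares crude adverse-event percentages although routine recording ends 30 days after last dose, so the comparison mixes exposure with risk if time on drug differs between arms

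*Protocol*

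**What the plan says.** Section 15.5 of the protocol fixes three things:

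- Population: "Safety analyses will include all randomised subjects who received at least one dose of study medication".
- Summary: "The frequency and percentage of patients experiencing a specific adverse event will be tabulated by treatment group".
- Test, for events judged clinically important: "a Chi-square test will be used to analyse the difference between the treatment groups".

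Section 12.1 sets the recording period: "from the first dose of Investigational Medicinal Product (IMP) to 30 days after the last dose of IMP should be reported as adverse events". Note 4 to Figure 1 repeats the limit: "adverse events need only be recorded if they occur within 30 days of the last dose of study medication". Section 12.4 has the same 30 days, or less if other anti-cancer treatment starts first. Section 12.1 adds an exception: a later event that the investigator considers possibly related is still reported.

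The study summary (section 2) lists "Safety and long-term tolerability of both regimens" as a secondary endpoint, and section 15.2 sets safety assessments at 2.75 and 5 years. No person-time or time-to-event summary is stated for safety.

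**The concern.** The denominator is fixed at one dose, but the time in which an event is routinely recorded depends on how long each woman stays on drug. Two arms with the same event hazard will show different percentages if one stops earlier.

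Several features make unequal time on drug plausible. The arms start on different drugs. Section 6.6 allows no dose modification, so unacceptable toxicity means stopping. Only arm A has a planned change of drug at 2.5-3 years. For women already enrolled, the GP letter for current participants foresees that some will decline the change: "Some patients may prefer to stay on tamoxifen in which case they will come" off study.

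The events most exposed to this are those that accrue over years. Section 3.4 names bone toxicity as an important issue for aromatase inhibitors, and fracture and osteoporosis are of that kind. A real excess could be diluted, or an apparent one produced, by time on drug alone.

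**Working it through.** Section 15.5 gives no event rate, stopping rate, significance level or power, so there is no stated figure to reproduce. All stopping rates below are assumptions. From the protocol: 4650 women per arm and the 2.75- and 5-year time points (section 15.2), and the 30-day window (section 12.1). Hazards are constant, stopping is independent of the event, and the test is a two-sided 5% comparison of two proportions by normal approximation.

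**1. Equal event hazard, unequal stopping.** With event hazard h, stopping hazard d, horizon T and W = 30/365.25 years, the recorded proportion is

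P = 1 − e^(−hW) × [ d/(d+h) × (1 − e^(−(d+h)T)) + e^(−(d+h)T) ].

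Take an event with 5.5% risk over 2.75 years of full exposure: h = −ln(0.945)/2.75 = 0.0206 per year. Stopping of 10% and 20% by 2.75 years gives d = −ln(0.90)/2.75 = 0.0383 and d = −ln(0.80)/2.75 = 0.0811. The recorded proportions are 5.38% and 5.10%, ratio 0.95, and the test rejects in 9.5% of trials.

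The ranges below cover 2.75-year risks of 3%, 5.5% and 16%; stopping is by the time point shown.

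| Time point | Stopping | Recorded ratio | Rejection |
|---|---|---|---|
| 2.75 y | 20% vs 20% | 1.00 | 5.0% |
| 2.75 y | 15% vs 20% | 0.97 | 5.6-8.6% |
| 2.75 y | 10% vs 20% | 0.95 | 7.4-19.5% |
| 2.75 y | 10% vs 30% | 0.89 | 15.7-62% |
| 5 y | 10% vs 20% | 0.95 | 9.5-32% |
| 5 y | 10% vs 30% | 0.89 | 25-87% |

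For an event with 16% risk, all of it in the first 3 months, 10% vs 20% stopping by 2.75 years gives 15.9% vs 15.8%. Early-onset events are hardly affected.

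**2. Masking of a real difference.** Table 3 gives clinical fracture in 3.1% on exemestane and 2.3% on tamoxifen in the Intergroup Exemestane Study, whose median follow-up was 30 months (section 3.3). This serves for scale only, because those women had already taken tamoxifen for 2-3 years. Hazards: −ln(0.969)/2.5 = 0.0126 and −ln(0.977)/2.5 = 0.0093 per year, ratio 1.35. Without the 30-day tail, the recorded proportion is P = λ/(λ+δ) × (1 − e^(−(λ+δ)T)), with T = 2.75.

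| Stopping by 2.75 y (exemestane vs tamoxifen) | Recorded | Ratio | Power |
|---|---|---|---|
| none | 3.41% vs 2.53% | 1.35 | 70% |
| 10% vs 10% | 3.23% vs 2.40% | 1.35 | 68% |
| 20% vs 10% | 3.05% vs 2.40% | 1.27 | 49% |
| 30% vs 10% | 2.87% vs 2.40% | 1.19 | 29% |

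**3. Bias in the other direction.** Use the formula of step 2 at T = 5, with equal hazards and 20% stopping by 5 years in both arms, and cut a fraction f of arm A off at 2.75 years. The ratio is arm B over arm A; rejection is for 5-year risks of 6%, 20% and 40%.

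- f = 2%: ratio 1.01; rejection 5.1% to 5.8%.
- f = 5%: ratio 1.02; rejection 5.7%, 7.3% and 10.1%.
- f = 10-20%: ratio 1.04-1.09; rejection 8-16%, 15-44% and 26-75%.

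Here arm B looks worse although nothing differs. In step 2 arm B looked better than it was.

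**The case against.** The strongest reply is that section 15.5 is an ordinary protocol-level safety paragraph, and a statistical analysis plan that is not at hand may already add exposure-adjusted rates. That is possible. But section 15.5 is not silent: it names the measure and the test, and those can be judged as they stand.

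A reader might infer more than the documents support, in four ways:

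- That the Chi-square test is invalid. It is a valid comparison of recorded proportions and keeps its 5% level when exposure is equal. It misleads only when read as a comparison of risk under unequal time on drug.
- That recording stops outright at 30 days. Section 12.1 still requires later events judged possibly related, and section 10.4 lists adverse events among items to record in follow-up. Only routine recording is limited. The exception depends on investigator judgement in an open-label trial, so it does not remove the problem.
- That stopping is known to differ. The protocol gives no stopping rates for this trial. The nearest figures, 1% stopping exemestane for drug-related reactions (section 3.4) and under 5% stopping tamoxifen for side effects (section 3.5), cover toxicity only and do not support gaps as wide as 10% vs 30%.
- That arm A loses recording time at the switch. This rests on a GP letter about existing participants. The letter says that women who decline will still be followed and analysed by intention to treat, and it does not say that their adverse-event recording stops. Section 6.1 makes the switch part of the allocated regimen.

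It is also fair to object that the direction of bias is not fixed. That stands: the point is susceptibility, not a demonstrated net bias.

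**Conclusion.** The point holds in a limited form. The stated comparison combines event risk with time on drug whenever time on drug differs between arms. That is plausible here but not documented, and the bias may go either way. At 15% vs 20% stopping the distortion is about 3%. At 10% vs 20% it is about 5% at equal hazard, and a fracture hazard ratio of 1.35 is shown as 1.27, with power falling from 70% (68% at equal 10% stopping) to 49%. A 2-5% extra exit from arm A gives rejection of only 5.1-10.1%. The larger figures need larger assumed gaps or very common events. All results assume constant hazards and stopping unrelated to the event. The issue matters most for late-accruing events and hardly at all for early-onset ones.

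**What to change.** Change section 15.5 as follows:

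- Keep the crude frequencies and percentages as description.
- Report patient-years at risk and time on treatment by arm.
- Base the comparison of clinically important events, above all late-accruing ones such as fracture and osteoporosis, on exposure-adjusted rates or on time to first event, censored at the end of the recording window.
- Give cumulative incidence at 2.75 and 5 years, with death and relapse as competing events.

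The cost is wording and one or two tables. Section 11 already requires the date of discontinuation on the case report form, so no new data are needed. Routine collection of events off drug is not proposed: section 15.1 describes seven separately managed country trials with their own forms and databases, so it would not clearly be cheap.

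The downside should be stated in the text. Censoring at the end of the window assumes that stopping is non-informative, which is doubtful when toxicity drives it. The result therefore describes on-treatment risk and should be read beside the crude table.

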### **15.6. Interim Analysis**

The entire TEAM trial will accrue a total of 9300 patients in order to observe 723 DFS events in the first co-primary endpoint at 2.75 years. Safety analyses will be reported to the Independent Data Monitoring Committee (IDMC) every 6 months without evaluation of efficacy. The number of efficacy events will be monitored centrally every 3 months and reported to the IDMB. One interim efficacy analysis is planned for the first co-primary endpoint, to be reviewed by the IDMC. As part of their evaluation of the progress of the trial, they will review an interim analysis of the combined TEAM trial at the time 50% of the events are reported for the first co-primary endpoint, at or before 2.75 years from the time of randomization when half of the required number of DFS events for the first co-primary endpoint have occurred. These unblinded data will only be reviewed by IDMC members. The primary objective of the interim analysis is the early detection of either alarming side effects, intolerability to the treatment regimens, or of large differences in treatment effects.

The overall alpha-level for the first co-primary analysis will be maintained at 0.0302 using an O'Brien-Fleming-type alpha-spending function. The levels of significance at the interim analysis and at the final analysis for the first co-primary endpoint are 0.0012 and 0.0298, respectively.

**15.7 Stratification**  
At randomisation, patients will be stratified by the following groups:

- ❑ **Nodal status:** node-negative, 1-3 positive nodes, 4 plus positive nodes
- ❑ **Prior chemotherapy:** none, anthracyclines, taxanes, other

## **16. DATA AND SAFETY MONITORING COMMITTEE (DSMC)**

The analyses will be supplied to an independent International DSMC who will be asked to give advice on whether the accumulated data from this trial, together with the results from other relevant trials, justifies the continuing recruitment of further patients. This committee will meet annually; depending on the rate of accrual and events rates. The DSMC will monitor recruitment to the trial and protocol compliance as well as tolerability and SAEs. The main outcomes will be analysed as stated in the analysis plan (Section 15).

## **17. ETHICAL REQUIREMENTS**

### **17.1. Ethical conduct of the study**

This study will be carried out in accordance with the World Medical Association (WMA) Declaration of Helsinki (1964) and the Tokyo (1975), Venice (1983), Hong Kong (1989), South Africa (1996) and Scotland (2000) amendments (Appendix 4). The declaration of Helsinki can be found on the World Medical Association website: <http://www.wma.net>

The protocol will be approved by a Multicentre Research Ethics Committee (MREC). Before entering patients into the study, the responsible Investigator must ensure that the protocol has also the approval of the relevant Local Research Ethics Committee (LREC).

The *TEAM* study office will send an annual trial update report to the MREC, which will also be forwarded to each participating centre, together with details of their individual recruitment. It will be the responsibility of each study site to send a copy of this report onto their LRECs.

### **17.2. Informed Consent**

It is the responsibility of the Investigator to obtain written Informed Consent (Appendices 7 & 8) in compliance with national requirements from each subject prior to entering the trial or, where relevant, prior to evaluating the subject's suitability for the study. The Patient Information Sheets will be available in electronic format from the CRCTU to enable individual hospitals to copy onto their headed paper.

Patient identification data (patient name and hospital number) will be required at randomisation to assist with long-term follow-up. The *TEAM* Steering Committee will preserve the confidentiality of patients taking part in this study.

### **17.3. Protocol amendment**

Any variation in procedure from that specified in the *TEAM* protocol may lead to the results of the trial being questioned and in some cases rejected. Any proposed protocol change must therefore be submitted in writing to the *TEAM* Steering Committee. All agreed protocol amendments will be documented by the CRCTU and will be submitted to the MREC for approval prior to submission to all LRECs. Changes not pre-approved by the *TEAM* Steering Committee will be considered as protocol deviations. This does not affect the individual clinician's responsibility to take immediate action if thought necessary to protect the health and interests of individual patients.

### **18. PUBLICATION POLICY**

The results of the pooled analysis will be published in the name of the *TEAM* trial in a peer reviewed journal on behalf of all collaborators. All presentations and publications, including abstracts, relating to the main trial must be authorised by the *TEAM* Steering Committee. The individual countries will be allowed to publish their efficacy results, however, the publication of efficacy results from the pooled analysis will take precedence over efficacy result publications of individual countries, unless the *TEAM* Steering Committee decides otherwise.

Individual countries will be encouraged to publish the results of their side-studies as soon as the data are mature. The Chief Investigator and Country Trial Steering Committee will have the responsibility to make decisions about publications of these results and authorship.

### **19. CONCURRENT STUDIES**

In the experience of the CRCTU, patients can be successfully randomised into multiple studies and, accordingly, *TEAM* patients can be offered the opportunity to participate in other appropriate randomised studies providing these have been approved by the appropriate Steering Committees. All Investigators will be kept up to date with information about ongoing national peer-reviewed studies.

### **20. SPONSORSHIP AND INDEMNITY**

The University of Birmingham is the sponsor for the *TEAM* study.

*TEAM* is co-ordinated by the CRCTU at The University of Birmingham. The CRCTU does not hold insurance against claims for compensation for injury caused by participation in a clinical trial and they cannot offer any indemnity. As this is a clinician-initiated study, The Association of the British Pharmaceutical Industry (ABPI) guidelines for patient compensation by the pharmaceutical industry will not apply. However, in terms of liability, NHS Trust and Non-Trust Hospitals have a duty of care to patients treated, whether or not the patient is taking part in a clinical trial. Compensation is therefore available in the event of clinical negligence being proven.

## APPENDIX 1: ECOG PERFORMANCE STATUS

Status	Description
0	Asymptomatic, fully active and able to carry out all pre-disease performance without restriction.
1	Symptomatic, fully ambulatory but restricted in physically strenuous activity and able to carry out performance of a light or sedentary nature e.g. light housework, office work
2	Symptomatic, ambulatory and capable of all self-care but unable to carry out any work activities. Up and about more than 50% of waking hours: in bed less than 50% of day.
3	Symptomatic, capable of only limited self-care, confined to bed or chair more than 50% of waking hours, but not bed-ridden.
4	Completely disabled. Cannot undertake any self-care. Totally bed-ridden.

## APPENDIX 2: Royal College of Pathologists Guidelines

National recommendations for assessment of steroid hormone positivity by immunostaining.

### Suggested scoring system

Score for proportion staining		Score for staining intensity	
0	No nuclear staining	0	No staining
1	<1% nuclei staining	1	Weak staining
2	1–10% nuclei staining	2	Moderate staining
3	11–33% nuclei staining	3	Strong staining
4	34–66% nuclei staining		
5	67–100% nuclei staining		

**Adding the two scores together gives a maximum score of 8.**

*(J Clin Pathol 2000; 53:634-635)*

## **APPENDIX 3: Pathological Marker Study**

### **Consenting Patients**

Patients who consent to participation in *TEAM* should also be made aware that, as an integral part of this trial, tissue removed at surgery will be used in research. It will be made clear in the Consent Form that this tissue will be used only for research and such use will in no way compromise or alter the patient's diagnosis or treatment. The total amount of tissue used in this research will be less than 1 g (approximately 30-50 mg). Tissue will be used for research related to the *TEAM* trial as defined in the following sections. At all times results from research studies will not be linked to patient notes.

### **HER-2 analysis**

HER-2 expression will be analysed using conventional immunohistochemistry (DAKO herceptest) on conventional tissue sections taken from the tissue block submitted by the local pathologist to the central laboratory. Sections will also be analysed for gene amplification using fluorescent in situ hybridisation. The results of the HER-2 analysis will be communicated back to the local hospital as this marker is now central to the management of many breast cancer patients.

